### 3. Comparisons with external data sources

Comparisons with external data sources includes comparing values to those recorded in the primary records as well as comparing rates, proportions, and distributions of variables across participating sites and to national, regional, or state data.

Comparison of extracted data to the primary records will be done on a limited basis, but can be informative for understanding flow of data into the data warehouse and appropriateness of structured data fields to the data of interest for this project. Appendix G includes some suggestions for data validation steps using primary medical or health records.

Variables for which rates, proportions, and distributions can be compared across participating sites and to national, regional, or state data include:

- Influenza vaccination coverage
- Respiratory virus testing and positivity
- Mechanical ventilation
- ICU admissions
- Proportion of patients with high-risk conditions

Westat will work with each site to review potential errors and decide on corrective action. In a few cases, sites may need to perform limited review of medical charts to clarify data elements flagged for review.

## **8.0 Ethical Considerations for Protection of Human Research Subjects**

### **8.1 Institutional Review Board Review**

Westat will serve as the single IRB of Record for this study for all participating sites and coordinating center for overseeing protections of human subjects research (45 C.F.R. § 46.114). The Westat IRB will enter into an IRB Authorization Agreement (IAA) that will include a communication plan with each institution prior to study implementation. IAAs and other documentation necessary in order to document compliance with the single IRB policy are maintained by Westat's IRB. Westat's IRB will use several mechanisms to communicate with sites, including email, phone calls and direct person-to-person communications as needed.

The protocol, data collection instruments, and other documents associated with the protocol shall be approved by Westat's IRB in compliance with all applicable laws, including 45 CFR 46. Subsequently, the protocol and related documents must be re-reviewed at least annually. Westat is responsible for preparation and submission of all documents and periodic reports required by the IRB and may seek input from sites regarding local implementation.

## **8.2 Patient Confidentiality**

All patients in the dataset will be assigned a linkable patient identification code (i.e. study identification code). Sites will be responsible for assigning and maintaining the link between the patient's identifying information and study ID. Documents maintaining this link will never be transferred to the coordinating center or study investigators. Personal identifiers (patient's name, address, medical record number, and encounter number) will exist at the participating site, as part of the hospital administrative data but will be replaced by a random generated code (linkable patient identification code), which will allow linkage of data without CDC or the coordinating center (Westat) having any access to these personal identifiers. All study data and administrative documentation will be identified by the study identification code only, to maintain participant confidentiality. Limited datasets will be created for the study; the study will comply with each institution's human subjects, privacy, and information security laws, if any. All study data files will be stored separately from any study records that contain names or other personal identifiers. All local databases must be secured with password protected access systems.

Listings that link study (and personal) IDs to other identifying information must be stored in a separate, locked file (or encrypted) in an area with limited access (or maintained in a directory separate from any study specific data files/sets) at each participating facility. Links between the study identification codes and personal identifiers will be destroyed by the

participating site after publication of the findings (for additional information please see the Data Management Plan, Appendix F).

Westat's Data Management Plan (Appendix F) details how Westat will protect any identifiers from improper use or disclosure, how Westat will destroy the identifiers after study completion, and how the protected health information will not be reused for other research.

### **8.3 Request for Waiver of Informed Consent**

The study relies on existing data already collected as part of patient's routine care or for billing purposes. No supplemental data collection will be done as part of this study. In addition, this study presents minimal risk to participants because there is no interaction or intervention with patients; therefore, a waiver of informed consent is requested. Minimal risk includes disclosure of clinical information on the patients' medical condition to persons outside of this protocol's defined study. Although patient information already available in the administrative databases will be collected, only information associated with a HIPAA limited dataset will be collected for the study. There is no risk to the participants' health from participation nor any impact on patients' current health care or therapeutic management plan because patients will not be contacted at any time. Consequently, patients will not be provided information about their participation.

Additionally, it will be impractical to conduct this study without waiving informed consent. By the time access to the datasets is available, most of the patients, if not all, will be out of the hospital (or some may have died during hospitalization), and the vast majority may have been hospitalized many years prior and may no longer live in the area or receive their care at the relevant study site. To contact each patient in this large, retrospective study for informed consent

or to notify them of study results would place an insurmountable burden on investigative staff and would prohibit successful completion of the study.

#### **8.4 Benefits to Participants**

There are no direct benefits for patients whose data contribute to this study. There may be future indirect benefits to the populations of the participating health systems, especially those with risk factors for severe illness from influenza. For example, information from this study may influence vaccination strategies for high-risk groups that may improve future outcomes for children, elderly adults, and those with high-risk conditions. In addition, understanding factors that make these groups at higher risk for influenza-associated hospitalization may help in developing and improving prevention and treatment guidelines.

#### **8.5 Data Records Lifecycle and Destruction**

Each participating study institution will store any paper study records in a physically secure location that is only accessible to authorized study staff. At close out, assuming no restrictions on data retention, the de-identified analytic files, documentation and all code used in processing will be archived in a way that would allow replication of the results. Each organization affiliated with the study, through subcontract or otherwise, must destroy data according to contractual specifications and must provide Westat with a certificate of destruction.

A certificate of destruction will be required for electronic and hard copy data and each must detail the type of data destroyed, how and when it was destroyed, and the signature of the authorized data security manager or corporate executive. In addition, any exceptions to the data destruction, e.g., data that must be maintained for internal records, must be identified in the certificate of destruction, along with a detailed rationale for why the data were not/could not be destroyed, at study conclusion.

## **8.6 Guidance for Decision Making**

A project steering committee will provide high-level input into this project, with CDC and Westat having final approval and sign off on any decisions made. The project steering committee will consist of two individuals from each site (decided by the site), a Westat representative, and a CDC representative. Each site will have one vote. The day-to-day overall project management will occur through the Westat study lead who will interface directly with CDC; however, the steering committee will be consulted on over-arching project issues including final protocol decisions, adjudicating any protocol deviations that might occur, reviewing and confirming analysis plans, and making final decisions on analyses, manuscripts, and authorship as needed. Upon the completion of all study deliverables, at a minimum, aggregate tables from publications of this collaboration will be publicly shared as specified in U.S. Government Data Sharing guidelines. Additional data may be publicly shared to further satisfy the U.S. Government Data Sharing guidelines, as determined by consensus of steering committee members and per site data use agreements.

## Appendix A: Outcomes, Exposures, and Modifiers for Study Objectives

| Objective   | Outcome Variables  | Exposure Variables   | Stratification Variables   | Confounders/Modifiers                              |
|---|--|--|--|--|
| Primary Objectives   |  |  |  |  |
| Objective 1:
Assess the validity and biases associated with defining the source population based on care-seeking. | Respiratory hospitalizations   | Cohort definitions
Healthcare utilization
Healthcare setting | High Risk Conditions
Insurance  | Age
Sex
Race
Ethnicity                    |
| Objective 2:
Determine the internal and external validity of data on influenza vaccination                        | Internal validity
Accuracy of derived vaccine status variable in relation to manual review of records
Contributions to conclusion about vaccination status by source
Consistency and completeness of vaccination data available by source

External validity
Comparison of vaccine coverage and data completeness to values from other studies | Data source

EHR

Registry
Billing/Admin. records   | Vaccination date

Vaccine type

Vaccine route

Vaccine lot number

Setting of administration

Num. of doses (<9 years) |  |
| Objective 3:
Assess biases associated with clinical testing for influenza and                                     | Proportion of cohort enrollees tested for influenza and other respiratory viruses
Types of influenza and other virus tests performed
Proportion of respiratory hospitalizations tested
Proportion of ARI outpatient visits tested   |  | Age

Healthcare setting
High-risk conditions 
Vaccination status   | Sex
Healthcare utilization
Race
Ethnicity |

| Objective   | Outcome Variables  | Exposure Variables | Stratification Variables   | Confounders/Modifiers   |
|---|--|--------------------|--|---|
| other respiratory viruses    |  |                    | Testing date
Timing of encounter
Discharge diagnosis codes   | Insurance coverage
Hospital length-of-stay   |
| Objective 4:
Measure incidence of health outcomes related to influenza by pediatric and adult age groups, influenza type/subtype, and high-risk conditions                | Laboratory confirmed influenza-associated respiratory hospitalizations
ICU admission
Invasive mechanical ventilation
In-hospital death

Outpatient/Urgent care visits |                    | Age
Influenza type/subtype
High-risk conditions  | Sex
Healthcare
Race
Ethnicity
Insurance coverage

Hospital length-of-stay     |
| Objective 5:
Estimate the effectiveness of current season influenza vaccine in preventing severe outcomes by age groups, influenza type/subtype, and high-risk conditions | Laboratory confirmed influenza-associated respiratory hospitalizations
ICU admissions
Outpatient/Urgent care visits (pediatrics)   | Influenza          | Age
Influenza type/subtype
High-risk conditions  | Sex
Healthcare
Race
Ethnicity

Insurance coverage

Hospital length-of-stay |
| Secondary Objectives   |  |                    |  |   |

| Objective  | Outcome Variables | Exposure Variables | Stratification Variables | Confounders/Modifiers |
|--|-------------------|--------------------|--------------------------|-----------------------|
| 
Objective 1:
Assess feasibility of defining underlying conditions using combination of ICD, medication, and lab data
                             |                   |                    |                          |                       |
| 
Objective 2:
Assess whether immunosuppression or use of immunosuppressive medications increases risk of severe outcomes or reduces VE
            |                   |                    |                          |                       |
| 
Objective 3:
Examine association between number and timing of priming doses with VE against outcomes in subsequent seasons (among children only)
 |                   |                    |                          |                       |

| Objective  | Outcome Variables | Exposure Variables | Stratification Variables | Confounders/Modifiers |
|--|-------------------|--------------------|--------------------------|-----------------------|
| Objective 4:
Examine association between prior season vaccination and current season VE (among adults only)  |                   |                    |                          |                       |
| Objective 5:
Determine measures of disease severity at hospital admission and assess impact on measures of VE  |                   |                    |                          |                       |
| Objective 6:
Measure incidence of secondary outcomes following influenza-related hospitalization   |                   |                    |                          |                       |
|  High-Risk Conditions: chronic lung disease, asthma, COPD, chronic metabolic disease, diabetes mellitus, blood disorders/hemoglobinopathy, cardiovascular disease, coronary artery disease, heart failure, congenital heart disease, neuromuscular disorder, neurologic disorder, immunocompromised condition, solid organ malignancy, hematologic malignancy, solid organ transplant, hematopoietic stem cell transplant, chronic renal disease, gastrointestinal/liver disease, rheumatologic/autoimmune condition, pregnancy (in woman of childbearing age), prematurity (in children <2 years of age). |                   |                    |                          |                       |
|  Influenza (all types/subtypes), respiratory syncytial virus, adenovirus, parainfluenza (1-4), human metapneumovirus, rhinoviruses/enteroviruses, coronaviruses, other novel viruses.  |                   |                    |                          |                       |

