### ***Influenza vaccine effectiveness to prevent severe influenza***

Influenza vaccination is the most important public health strategy to prevent influenza illness and vaccination is recommended annually for all people aged 6 months or older in the United States. However, influenza VE varies from season to season, and across different age and risk groups. A growing body of research points to the effectiveness of influenza vaccination in preventing influenza-associated hospitalizations and other severe outcomes, such as admission to the ICU and in-hospital death. While these studies have begun to explore the benefits of vaccination in reducing the risk of influenza-related severe outcomes, with some studies suggesting that the vaccine is more effective in reducing severe disease than reducing infection, the data are largely inconclusive as most are insufficiently powered or not designed to examine and stratify VE by high-risk groups, including children, older adults and those with chronic conditions.

Of the recent studies, Thompson, et al., examined hospitalized adults over multiple influenza seasons found that influenza vaccination decreased influenza-related hospitalizations by 37%, and reduced ICU admission for influenza-related complications by 82%. Analysis of influenza-positive hospitalized adults in the United States also suggests 37% reduction in odds of ICU admission among those vaccinated for influenza. Similarly, studies have shown that influenza vaccination can decrease children's risk of admission to the pediatric intensive care unit by as much as 74% and influenza-associated mortality by 65%. Studies of influenza VE

among those at high risk for influenza-associated complications are rare, with the exception being pregnant women for whom several studies have demonstrated effectiveness of influenza vaccination against influenza infection during pregnancy and in the neonate.

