**5.5 Outcomes of Interest**

- Respiratory illness-associated hospitalizations with laboratory-confirmed influenza
  - Respiratory hospitalizations will be defined using ICD-9 and ICD-10 discharge diagnoses codes as listed in Appendix D.
  - Data on all respiratory hospitalizations will be collected for the entirety of the surveillance period (influenza season).
  - The respiratory hospitalizations will be linked with data on influenza testing to determine if the hospitalization was associated with laboratory-confirmed influenza.
    - Laboratory-confirmed influenza associated respiratory hospitalization will be defined by a positive influenza test within 14 days prior to hospitalization or no more than 3 days after hospital admission.

- Hospitalization will be defined as admission to an inpatient ward or an observation unit. Time spent only in the emergency department will not count as a hospitalization.
- Re-admissions that occur within 30 days of the index hospitalization will be counted as part of the index hospitalization. Readmissions that occur >30 days after the index hospitalization will be considered new hospitalization events.
- ICU admission among persons hospitalized with laboratory-confirmed influenza-associated respiratory hospitalization
- Invasive mechanical ventilation among persons hospitalized with laboratory-confirmed influenza-associated respiratory hospitalization
- In-hospital death among persons hospitalized with laboratory-confirmed influenza-associated respiratory hospitalization
- Acute respiratory illness-associated outpatient visits with laboratory-confirmed influenza
  - Acute respiratory illness-associated outpatient visit will be defined using the ICD-9 and ICD-10 discharge codes listed in Appendix D.
  - Data on all acute respiratory illness-associated outpatient visits will be collected for the entirety of the surveillance period (influenza season).
  - The acute respiratory illness outpatient visit will be linked with data on influenza testing to determine if the visit was associated with a positive influenza laboratory test.

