## **5.6 Summary of Data Elements for Primary Objectives**

Please see Appendix B for more detailed list of data elements

[figure not shown]
- For the entire cohort:

- Demographic information (age, sex, race, ethnicity)
- Date of enrollment in health plan and/or date of first encounter in the health system in the 12 months before the start of influenza season (as applicable)
- Healthcare utilization (primary/secondary insurance type, number of medical encounters before and during influenza season). This is further defined to be the monthly number of healthcare encounters by setting (general practice, medical specialty, emergency department, urgent care, telehealth, or inpatient).
- Underlying high risk medical conditions (derived from ICD codes)
- Vaccination status (influenza and other vaccinations received dating back to 2010)
- All hospitalizations and outpatient encounters with respiratory virus testing during influenza season of interest:
  - Date of encounter (or date of admission)
  - Date of testing
  - Clinical setting
  - Influenza and other respiratory virus test type and result
  - Diagnosis codes from the encounter/admission
- Respiratory syndrome-associated hospitalizations during influenza season of interest:
  - Hospital admission and discharge dates
  - Diagnosis codes
  - Severe outcomes (ICU admission, mechanical ventilation, in-hospital mortality)
- ARI syndrome-associated outpatient encounters during influenza season of interest
  - Encounter date
  - Diagnosis codes

Data streams for entire cohort during to-be-determined lead-in period:

[figure not shown]

Data streams for influenza season of interest:

[figure not shown]

All sources should be linked by subject ID  
 \*For influenza and other vaccinations received dating back to 2010, where possible.

Data streams for entire cohort during to-be-determined lead-in period:

Data streams for influenza season of interest:

All sources should be linked by subject ID  
 \*For influenza and other vaccinations received dating back to 2010, where possible.

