***Objective 4: Measure incidence of health outcomes related to influenza***

- Incidence of laboratory-confirmed influenza-associated respiratory hospitalizations will be calculated by dividing the number of respiratory hospitalizations associated with a positive influenza laboratory test observed during each study season by the person-time of the cohort at risk during the corresponding season.
  - This will be calculated for the following risk groups: age group, high-risk conditions, vaccinated for influenza, unvaccinated, race/ethnicity, socio-economic status, etc.
  - Incidence will be compared between risk groups using rate differences or relative rates

- Incidence of ICU admission, mechanical ventilation, and in-hospital death associated with influenza will be similarly calculated, with the respective numerators restricted to those laboratory-confirmed influenza-associated respiratory hospitalizations with the relevant outcomes identified.
  - This will be calculated for the following risk groups where sample size permits: age group, high-risk conditions, vaccinated for influenza, unvaccinated, race/ethnicity, socio-economic status, etc.
  - Incidence will be compared between risk groups using rate differences or relative rates
- Incidence of laboratory-confirmed influenza-associated acute respiratory illness (ARI)-associated outpatient visits will be calculated by dividing the number of ARI visits with a laboratory test positive for influenza observed during each study season by the person-time of the cohort at risk during the corresponding season.
  - This will be calculated for the following risk groups where sample size permits: age group, high-risk conditions, vaccinated for influenza, unvaccinated, race/ethnicity, socio-economic status, etc.
  - Incidence will be compared between risk groups using rate differences or relative rates

As multiple events are possible during a season, incidence estimates throughout this objective may be calculated in two ways: 1) counting only the first occurrence, and 2) counting the cumulative number across the season.

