***Objective 5: Assessment of vaccine effectiveness***

- We will estimate the effect of influenza vaccination on risk of lab-confirmed influenza-associated respiratory hospitalization by age group, influenza type/subtype, and high-risk conditions
  - The risk of influenza-associated respiratory hospitalization among cohort members who were or were not vaccinated with the current season influenza will be compared using appropriate methods for longitudinal data with time varying exposure, including Poisson regression or proportional hazards modeling.
  - VE will be estimated as  $(1 - \text{adjusted relative risk}) \times 100$ .
  - We will assess and adjust for confounders as appropriate. These may include characteristics such as age, sex, site, race/ethnicity, high-risk health conditions, prior healthcare utilization, time of event during the influenza season, etc.
  - Data collected for this study are intended to be pooled across sites. VE will first be estimated for each site and heterogeneity in estimated VE across sites examined.
- We will estimate the effect of influenza vaccination on risk of lab-confirmed influenza-associated ARI outpatient visit among children (adults only if influenza testing allows for this) by age group, influenza type/subtype, and high-risk conditions
  - The risk of influenza-associated outpatient visits among cohort members who were or were not vaccinated with the current season influenza will be compared using appropriate methods for longitudinal data with time varying exposure, including Poisson regression or proportional hazards modeling.
  - VE will be estimated as  $(1 - \text{adjusted relative risk}) \times 100$ .

- We will assess and adjust for confounders as appropriate. This may include characteristics such as age group, sex, site, race/ethnicity, high-risk health conditions, prior healthcare utilization, time of event during the influenza season, etc.
- Data collected for this study are intended to be pooled across sites. VE will first be estimated for each site and heterogeneity in estimated VE across sites examined.
- VE analyses against influenza-associated respiratory hospitalizations will also be conducted using a test-negative case-control design
  - This analysis will be conducted among individuals who were hospitalized for acute respiratory illness during the influenza season and who were tested for influenza.
  - Cases will be defined as hospitalized individuals who tested positive for influenza.

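### Appendix A lists hospital length of stay as a confounder or modifier for Objectives 4 and 5, although it is fixed only after the hospitalization outcome and section 6.1 does not name it

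*Protocol*

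**What the plan says.** - **Appendix A**, rows for primary Objectives 4 and 5, lists "Hospital length-of-stay" under Confounders/Modifiers. The outcomes in those rows include influenza respiratory hospitalization itself, ICU admission, and outpatient or urgent care visits.
- **Section 7.2** describes Appendix A as listing the analytic variables needed for the primary objectives. **Section 4.1** describes it as giving the main outcomes, exposures and modifiers.
- **Section 5.6** collects "Hospital admission and discharge dates" for respiratory hospitalizations in the season of interest. Length of stay can only come from these.
- **Section 5.5** confirms the outcome by a "positive influenza test within 14 days prior to hospitalization or no more than 3 days after hospital admission".
- **Section 6.1, Objective 4** divides events "by the person-time of the cohort at risk during the corresponding season". It then states: "Incidence will be compared between risk groups using rate differences or relative rates".
- **Section 6.1, Objective 5** compares vaccinated and unvaccinated cohort members by "appropriate methods for longitudinal data with time varying exposure, including Poisson regression or proportional hazards modeling", and adds a test-negative analysis among tested inpatients. For each analysis it says "We will assess and adjust for confounders as appropriate" and gives an open list of examples. Length of stay is in none of these lists.
- **Section 3.1** reports that an analysis of influenza-positive inpatients "also suggests 37% reduction in odds of ICU admission among those vaccinated for influenza".

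**The concern.** A confounder must be able to precede or share causes with both exposure and outcome, and a baseline modifier must exist before the outcome. Length of the index stay does neither. It starts when the outcome event starts and is complete only at discharge. By the protocol's own severity evidence, it may be affected by vaccination.

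Two things are at stake. In the cohort analysis, a variable that exists only for admitted people can remove or redefine the comparison. In the test-negative analysis, where everyone has a stay, VE by length of stay can look like effect modification when it reflects the vaccine's effect on severity. An analyst at a site or at the coordinating centre who builds the model from Appendix A rather than from section 6.1 could meet either problem.

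**Working it through.** The protocol states no figure that depends on length of stay, so there is none to reproduce. The check has three parts.

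**1. Timing and definition.** Vaccination counts only if given at least two weeks before the event (section 5.4). The event is an admission, with laboratory confirmation no later than 3 days after it. The stay ends at discharge. The order is therefore vaccination, admission, completed stay. The Objective 4 denominator and the Objective 5 cohort model cover all members, and those never admitted have no stay. An outpatient visit need not have one either.

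**2. Cohort model.** I used one simulated cohort of 400,000.
- Coverage from section 6.2: (30% + 42% + 65%)/3 = 45.7%.
- True VE 40%, a level in Table 1.
- Assumed: influenza hospitalization risk 0.4% in the unvaccinated, other respiratory hospitalization risk 2%.

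Poisson regression gave:

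| How length of stay is entered | People used | VE |
|---|---|---|
| Not entered | 400,000 (1,360 events) | 45.2% |
| Influenza admissions only, complete cases | 1,360, all events | 0% |
| Indicator of a stay, influenza admissions only | 400,000; indicator equals outcome, SE about 17,000 | 0% |
| All respiratory admissions, complete cases | 9,411 | 41.7% |
| Indicator of a stay, all respiratory admissions | 400,000; stay coefficient diverges | 41.6% |
| Set to 0 if not admitted, linear | 400,000 | 44.9% |

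The 45.2% differs from 40% by sampling error in a single dataset, so the rows should be compared with each other. In the fourth row 9,411/400,000 = 2.4% of the cohort remains. In the fifth row, members without a stay have no events, so the vaccine estimate again comes from inpatients only. The expected effect of that restriction, before any stay term, follows from the inputs:
- Influenza share of admissions, unvaccinated: 0.004/(0.004 + 0.996 × 0.02) = 0.167.
- Influenza share of admissions, vaccinated: 0.0024/(0.0024 + 0.9976 × 0.02) = 0.107.
- Ratio 0.642, so VE 35.8% instead of 40%.

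**3. Test-negative model.** True odds ratio 0.60, no baseline modifier, stay among controls unrelated to vaccination. Let p be the long-stay share in unvaccinated cases and g the odds ratio for a long stay, vaccinated against unvaccinated cases. The long-stay share in vaccinated cases is q, where q/(1 − q) = g·p/(1 − p). Then

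- long-stay odds ratio = 0.60 × q/p
- short-stay odds ratio = 0.60 × (1 − q)/(1 − p)

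The protocol gives no effect of vaccination on length of stay. I took g = 1 − 0.37 = 0.63 from the ICU evidence as a proxy. With p = 0.40: q = 0.42/1.42 = 0.296, long-stay odds ratio 0.60 × 0.296/0.40 = 0.444 (VE 55.6%), short-stay odds ratio 0.60 × 0.704/0.60 = 0.704 (VE 29.6%).

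For p = 0.20, 0.40 and 0.60, with adjusted VE from a main-effects logistic model (assumed 40% long stays in controls, 25% of those tested are cases):

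| g | VE, short stay | VE, long stay | Adjusted VE |
|---|---|---|---|
| 1 | 40.0% | 40.0% | 40.0% |
| 0.63 | 22.9–35.2% | 51.4–59.2% | 39.0–40.9% |
| 0.40 | 6.3–31.8% | 62.5–72.7% | 38.5–41.6% |

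The largest shift in overall VE is 41.6 − 40.0 = 1.6 points.

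**The case against.** The strongest reply is that nothing in the protocol commits an analysis to length of stay. Section 6.1 is the operative plan. Its lists are permissive and name only characteristics that precede the outcome, plus the timing of the event. VE is to be broken down by age, influenza type or subtype, and high-risk condition. The steering committee confirms analysis plans (section 8.6). This stands, and it limits the point to a wrong entry in an appendix. It does not clear the entry: section 7.2 gives Appendix A the standing of a list of needed variables, and no passage confines length of stay to description.

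A reader might go further and infer that the entry makes the cohort model impossible to fit. The documents do not support that. Section 5.6 collects dates for all respiratory hospitalizations, and with those data several codings run and return a VE. Collapse needs stay to be known for influenza admissions only.

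A reader might also infer that the test-negative analysis must show false modification. It does so only if vaccination changes stay among cases; with g = 1 nothing appears. The cited evidence concerns ICU admission, not stay. Moreover, when stay among controls is unrelated to vaccination, the long-stay value is a valid VE against long-stay influenza hospitalization. The error would lie in reading it as modification by a patient characteristic. Section 4.2 does plan to study severity and VE, but using severity at admission.

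**Conclusion.** The entry is wrong and should be corrected. Length of stay cannot be a confounder or a baseline modifier for either objective, and Appendix A disagrees with section 6.1. That conclusion rests on the protocol's own definitions and needs no assumption.

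The harm is conditional on someone using the entry. In the cohort analysis it ranges from almost none (length of stay set to 0 for the non-admitted, linear) to an inpatient-only estimate or a VE of 0%, depending on coding. In the test-negative analysis, under the assumed odds ratio of 0.63 and true VE of 40%, VE would be about 23–35% in short stays and 51–59% in long stays, with overall adjusted VE moving by about 1–2 points at most across the scenarios. Incidence, long-stay shares, case share and the effect of vaccination on stay are all assumptions, and the cohort figures come from one simulated dataset.

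For Objective 4 the entry is mainly a mislabel, because section 6.1 names no adjusted model there. The documents do not support a claim that the planned VE results are already biased.

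**What to change.** Delete length of stay from the Confounders/Modifiers cells for Objectives 4 and 5 in Appendix A. Alternatively, if it is of interest, move it out of that column and label it a descriptive severity outcome among inpatients. Either change brings Appendix A into line with section 6.1.

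No general rule on when covariates must be measured is needed. A rule requiring measurement before September 1 would exclude the calendar timing of the event, which section 6.1 properly lists.

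The cost is an edit to two table cells. No data collection changes, since admission and discharge dates are still needed to describe hospitalizations.
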